Iron chelation use	Baseline Characteristic; Covariate	[Baseline]	Frequency and proportion (N, %)
Delayed hemolytic transfusion reactions	Baseline Characteristic; Covariate	[Baseline]	Frequency and proportion (N, %)
Alloimmunization	Baseline Characteristic; Covariate	[Baseline]	Frequency and proportion (N, %)
Death	Baseline Characteristic; Covariate	[Follow-up]	Frequency and proportion (N, %)
Voxelotor discontinuation	Baseline Characteristic; Covariate	[Follow-up]	Frequency and proportion (N, %)

Abbreviations: ESA: Erythropoietin Stimulating Agent; RBC: Red blood cell; SCD: Sickle cell disease.

Baseline genotype will not be included in the PS model because patients commonly have multiple values due to coding/billing errors and this value is more likely to be misclassified. The most frequently occurring value (not including unknown/other) will be selected

- 2. SCD-specific comorbidities include the following: acute chest syndrome, acute coronary syndrome, acute osteomyelitis, acute renal failure, aplastic crisis, intracerebral and subarachnoid hemorrhage, myocardial infarction, priapism, splenic sequestration crisis, transfusion-associated reaction, venous thromboembolism, avascular necrosis, cholelithiasis, chronic kidney disease, chronic pain, diabetes, heart failure, iron overload, leg ulcer, pulmonary hypertension, VOC, and retinopathy.
- 6. Given feasibility analyses have indicated a low proportion of patients (<25%) have lab values, Hb will be excluded from the PS model. Hb will be evaluated excluding those measurements within 2 days of an acute event or within 30-60 days of a transfusion event. Full algorithm will be provided in a separate statistical analysis plan.
- 4. CCI categories include: myocardial infarction, congestive heart failure, peripheral vascular disease, cerebrovascular disease, dementia, chronic pulmonary disease, rheumatic disease, peptic ulcer disease, mild liver disease, diabetes without chronic complication, diabetes with chronic complication, hemiplegia or paraplegia, renal disease (mild to moderate), renal disease (severe), any malignancy without metastasis including leukemia and lymphoma, moderate or severe liver disease, metastatic solid tumor, human immunodeficiency virus, acquired immunodeficiency syndrome

The table above includes a summary of baseline characteristics and possible covariates for PS modeling. Covariates will be selected using the diagnostic criteria outlined in the data analysis plan (Section 9.7).

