Table 5. Description of Endpoints and Alignment to Study Objectives

Endpoint	Assessment Period	Output	Objective Alignment
Change in RBC transfusions	[Baseline]; [Follow-up]	Mean change in the number of RBC transfusions (maximum 1 per day) PPPY from baseline to follow-up	Primary Objective
VOCs	[Baseline]; [Follow-up]	Mean change in the number of events (maximum 1 per day) PPPY from baseline to follow-up. VOC events need to occur more than 5 days apart to be considered separate events.	Exploratory Objective 1.1
ACS	[Baseline]; [Follow-up]	Mean change in the number of events (maximum 1 per day) PPPY from baseline to follow-up	Exploratory Objective 1.1
ACS Including Pneumonia	[Baseline]; [Follow-up]	Mean change in the number of events (maximum 1 per day) PPPY from baseline to follow-up	Exploratory Objective 1.1
Priapism	[Baseline]; [Follow-up]	Mean change in the number of events (maximum 1 per day) PPPY from baseline to follow-up	Exploratory Objective 1.1

Voxelotor

V2.0 23 December 2024		9	
Stroke (including transient ischemic attack)	[Follow-up]	Time to event during follow-up	Exploratory Objective 1.2
RBC transfusions in follow-up	[Follow-up]	Mean number of RBC transfusions (maximum 1 per day) PPPY in follow-up	Exploratory Objective 2
Percent reduction in RBC transfusion > 30%	[Baseline]; [Follow-up]	Proportion of patients with a percentage decrease in the number of RBC transfusions (maximum 1 per day) PPPY from baseline to follow-up that is greater than 30%	Exploratory Objective 2
Zero RBC transfusions in follow-up	[Follow-up]	Proportion of patients with 0 RBC transfusions (maximum 1 per day) PPPY during follow- up	Exploratory Objective 2
Iron overload	[Follow-up]	Time to event during follow-up	Exploratory Objective 3
Iron chelation use	[Follow-up]	Time to event during follow-up	Exploratory Objective 3
Delayed hemolytic transfusion reactions	[Follow-up]	Time to event during follow-up	Exploratory Objective 3
Alloimmunization	[Follow-up]	Time to event during follow-up	Exploratory Objective 3
Composite outcome (iron overload, iron chelation use, delayed hemolytic transfusion reactions, and/or alloimmunization)	[Follow-up]	Time to event during follow-up	Exploratory Objective 3

Abbreviations: ACS: Acute Chest Syndrome; PPPY: per patient per year; RBC: Red blood cell; VOC: vaso-occlusive crisis The table above includes a summary of the outcomes of interest for this analysis. Operational definitions can be found in the data analysis plan (Section 9.7).

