9.7.2. Baseline Balance

PS methods will be used to account for baseline balance of covariates between the treated group and matched controls. PS adjustment allows for the inclusion of a pre-defined comprehensive list of confounding covariates to ensure comparable exposure and referent groups, avoiding non-convergent issues of standard outcome models. PS models estimating the ATT will be considered for this analysis. An iterative approach to estimating the PS will be used.

PS Estimation

Potential covariates that affect treatment decisions or outcomes and are eligible for inclusion in the PS model are listed in Table 5.³⁰ Potential confounding covariates will be assessed for balance at baseline using absolute standard differences (ASD). Covariates with an ASD > 0.1 will be considered imbalanced and will be included in a PS model fit using logistic regression. With this approach, the PS will be modeled as the conditional probability of receiving voxelotor given the selected covariates for each individual. The PS modeling will be performed blinded of any outcome to ensure endpoints will not be assessed before a PS method is selected. Diagnostic criteria used to assess PS model estimate are described below and in Table 6. Multiple iterations of the PS model estimation may be performed depending on diagnostic evaluation results.

Use of PS in Baseline Confounder Balance

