Annex Table 3. Addressing Potential Real-World Data Limitations and Concerns

Variable	Potential concern	Supportive Data and/or Rationale	Study Design Mitigation
RBC transfusion outcome	Misclassification bias	Gu et al. found that 42,106 out of 46,381 (91%) RBC transfusion medical records in patients with SCD from Optum documented having a medical claim. Random sample of 200 RBC transfusion episodes were reviewed with associated free text notes. Of the 200 RBC transfusions, 181 (90.5%) had documentation of an RBC transfusion within 3 days of the procedure claim. ¹	Medical claims data will be used to measure the RBC transfusion outcome in this study. Prior studies support that medical claims are an accurate source for RBC transfusion, and no evidence exists of misclassification bias. If missingness occurred, no theoretical basis for differential misclassification between exposed/unexposed groups exists.
Hydroxyurea exposure	Known confounder	Hydroxyurea increases hemoglobin F and has demonstrated in clinical studies to decrease the proportion of individuals with SCD to receive at least 1 RBC transfusion.	captured from pharmacy prescription claims. Patients are required to have continuous enrollment in their pharmacy and medical benefits, so limited missing data should exist for hydroxyurea claims. Hydroxyurea will be included in the propensity score model as a covariate and both groups will have similar prior exposure to hydroxyurea. Similarly, as a sensitivity analysis will be performed to report the results stratified by prior treatment exposure to hydroxyurea,
Covariates	Misclassification bias	There is a possibility of missing information for patients is expected to be low but possible if patients seek healthcare without the use of medical or pharmacy insurance.	crizanlizumab, L-glutamine, and/or ESA. Since all patients regardless of exposure status will be required to have continuous enrollment over the period that covariates will be assessed if missingness occurred, no theoretical basis for differential misclassification between exposed/unexposed groups exists.

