Hb labs	Missingness	Based on preliminary data explorations, approximately 17% of patients have at least one Hb result during the study timeframe. All lab values have an associated date and time.	Due to missingness in Hb lab results, Hb cannot be adjusted for in the primary analysis; however, a sensitivity analysis is planned that will stratify by baseline Hb and a separate propensity score model will be used to adjust for Hb results.

SCD genotype	Missingness	It is more likely severe genotypes (e.g., HbSS) should be requiring more than 2 RBC transfusions in the past year.	RBC transfusion by SCD genotype will be assessed in sensitivity analysis.
		Based on preliminary data explorations, approximately 93% have patients have genotype documented in our data set.	
Comorbidities	Missingness	There is a possibility of missing information for patients is expected to be low but possible if patients seek healthcare without the use of medical or pharmacy insurance.	Continuous enrollment in a health plan is required as part of the analysis. Thus, all healthcare interactions through insurance will be captured and including documented comorbidities recorded in medical billing records. If missingness occurred, no theoretical basis for differential documentation between exposed/unexposed groups exists. Propensity score adjustment aggregates the probability of exposure to voxelotor. It is expected that more severe diseases that would have a larger impact on outcomes would be better captured in the data ² and that limited underreporting of non-severe comorbidities should not have a substantial impact on the overall results.
Treatment adherence	Missingness	These data are not missing. Komodo data has near 100% of patients' pharmacy claims when requiring patients to have continuous enrollment in the pharmacy benefit. For exposed patients, we have 100% of the voxelotor claims through the use of Claritas data.	including as-treated and intent- to-treat analysis to ensure consistent results that best represent a RCT.
Race/ethnicity	Unmeasured confounder	Based on preliminary data explorations, approximately 90% of SCD patients have documented race/ethnicity in our data set. CDC estimates more than 90% are non-Hispanic Black or African American, and an estimated 3%–9% are Hispanic or Latino.	and is not missing from our data set.

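### The ASD > 0.1 entry rule can leave known baseline confounders out of the propensity score, against Annex Table 3, and the covariate tables it draws on are mislabelled

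*Protocol*

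**What the plan says.** The entry rule is in Section 9.7.2, PS Estimation: "Covariates with an ASD > 0.1 will be considered imbalanced and will be included in a PS model fit using logistic regression". The PS is then modelled on the covariates so selected. The same section justifies PS adjustment by its ability to take in a full set of confounders named in advance.

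Annex Table 3 calls hydroxyurea a known confounder and says: "Hydroxyurea will be included in the propensity score model as a covariate". It attaches no condition. Section 9.9 adds that visit frequency and provider type will matter for the PS model.

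On the candidate list, Section 9.7.2 says that potential covariates "eligible for inclusion in the PS model are listed in Table 5". That table is headed "Table 5. Description of Endpoints and Alignment to Study Objectives". The evident target is Table 4, whose note reads: "The table above includes a summary of baseline characteristics and possible covariates for PS modeling". Table 4 gives a covariate role to follow-up time, death and "Voxelotor discontinuation", all assessed in follow-up only. Figure 1 sets the covariate window at [-365, 0].

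Table 6, item 3, re-checks all potential confounders after matching, with ASD up to 0.10 counted as balanced. A small residual imbalance may be accepted if clinical experts judge that the variable does not predict the outcome. Otherwise the variable goes into the outcome model.

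On genotype, the Table 4 footnote says: "Baseline genotype will not be included in the PS model because patients commonly have multiple values due to coding/billing errors". Annex Table 3 says "approximately 93% have patients have genotype documented in our data set" and promises a sensitivity analysis by genotype.

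**The concern.** A PS covariate should be chosen because it is a baseline confounder, not because it happens to differ between the arms before adjustment. The screen makes entry depend on a sample difference, so a variable that the protocol itself calls a confounder can be left out. Matching on the remaining variables can then unbalance it.

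Baseline transfusion count is the variable least suited to this treatment. The primary outcome in Section 9.7.3 is the follow-up rate minus the baseline rate, so the baseline count is part of the outcome by construction.

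The table errors add a second difficulty. Taken literally, one candidate list consists of endpoints and the other contains events after index. Neither can be applied as printed to the model behind the primary estimate.

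**Working it through.** **The plan's own figure.** The only design figure is 80% power with 185 treated and 370 controls (difference 1, SD 3.0, factor 1.65). With a two-sided alpha of 0.05 (assumed, as none is stated), the treated number is 1.5 × (3.0 × (1.960 + 0.842))² = 106. Then 106 × 1.65 = 175, below 185, and power at 185 is about 0.82. The figure holds and this point does not touch it.

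**Entry rule against annex.**

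| Baseline hydroxyurea | Section 9.7.2 | Annex Table 3 |
|---|---|---|
| ASD above 0.1 | enters | enters |
| ASD 0.1 or less | does not enter | enters |

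The conflict is conditional, but the condition is an ordinary one. The rule does not contain the word only. It is nevertheless the only selection rule given, and Section 9.3 says that covariates are selected by the Section 9.7 criteria.

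**Does balance before adjustment justify omission?** This is a constructed example, not study data. Let X1 be in the PS, with mean 0.5 in the treated and 0 in controls, SD 1. Let X2 have mean 0 in both arms, SD 1, and correlation ρ with X1 within each arm. The marginal ASD of X2 is 0, so the rule leaves it out. SMR weights on X1 move the control mean of X1 from 0 to 0.5, and X2 moves with it by ρ × 0.5. The treated mean of X2 stays at 0.

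| ρ | ASD of X2 after, 0.5 × ρ | Simulated: before | Simulated: after |
|---|---|---|---|
| 0.3 | 0.15 | 0.001 | 0.149 |
| 0.5 | 0.25 | 0.019 | 0.267 |
| 0.7 | 0.35 | 0.007 | 0.343 |

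A covariate can therefore pass the screen and exceed 0.10 after adjustment. The example uses the fallback weighting. Matching on X1 aligns its distribution in the same way.

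**What the Table 6 re-check catches.** It would flag all three rows above if X2 is a listed covariate. It would not act on a confounder ending at or below 0.10, and it allows acceptance by judgement above that.

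**Timing of covariates.** Table 4 gives three rows a covariate role with a follow-up period. Figure 1, Section 9.7.1 and the baseline wording of Section 9.7.2 restrict covariates to the period up to index, and Section 9.7.3 speaks of covariates before index. If the labels were followed, a discontinuation flag that is zero in all controls has ASD = √(2p/(1−p)), where p is the proportion of voxelotor patients who discontinue. That is 0.14 at p = 1% and 0.47 at p = 10%, so the screen alone would not stop it.

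**Genotype.** The Table 4 footnote excludes it from the PS for misclassification. Section 9.9 lists genotypes among characteristics not all available. Annex Table 3 gives about 93% documented and promises a sensitivity analysis. Table 7 lists none.

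**The case against.** The best defence of the screen is that it does not have the last word. PS estimation is iterative, balance is re-checked after matching for all potential confounders and not only those in the model, and a residually imbalanced outcome predictor is carried into the outcome model. That stands, and it narrows the concern. It does not answer the conflict with the annex, and it repairs afterwards what prespecified entry would avoid.

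On the follow-up rows, a reader might infer that post-index variables are certain to enter the PS and that discontinuation would separate the arms perfectly. The documents do not support either. Figure 1 and the baseline wording show a pre-index intent. PS modelling is blinded to outcomes, which keeps follow-up transfusions out. Section 9.7.2 and Table 6 also allow variables with zero cells or extreme coefficients to be dropped. Voxelotor patients who continue share the value zero with controls, so separation is not perfect. The follow-up period shown on the drug rows can be read as a reporting period. What stands is a contradiction in labels and a wrong table number.

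On genotype, a reader might infer that the annex claims control of a variable that the PS drops. The readable annex text promises only a sensitivity analysis, and the severity row is cut off. The stated reason for exclusion is coding error, which a high documentation rate does not answer. Exclusion is a reasoned choice that statisticians could dispute, and Table 4 offers other severity markers. Only the inconsistencies stand.

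**Conclusion.** The entry rule should be changed. It conflicts with Annex Table 3 and with the section's own rationale, and marginal balance is not a sound reason to omit a prespecified confounder. Whether any confounder would in fact be dropped depends on ASDs that the protocol does not report.

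No bias is quantified. A reader might multiply a residual ASD by an assumed outcome correlation: one covariate at ASD 0.10, correlation 0.1 to 0.5 and SD 3.0 gives 0.03 to 0.15 transfusions per patient per year, against a design difference of 1. The correlations are assumptions, and an imbalance of 0.10 would also pass the post-adjustment check that the fix retains. These figures are therefore not the error that the change removes.

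The wrong table reference and the three mislabelled rows are contradictions to correct, not evidence that post-index variables will be used. The genotype statements need reconciling only. The SAP may settle some of this, but the protocol statements conflict as they stand.

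**What to change.** - In Section 9.7.2, enter all prespecified baseline confounders in the PS regardless of ASD, subject to the existing overfit and positivity checks. Name at least baseline transfusion count, hydroxyurea and the other SCD drugs, VOC and ACS, healthcare utilisation and hematology care. Use ASD only as the post-adjustment diagnostic.
- Cite Table 4 instead of Table 5, and state that PS candidates are limited to variables measured on or before index.
- In Table 4, relabel follow-up time, death and voxelotor discontinuation as descriptive. Mark follow-up values of the drug and transfusion rows in the same way.
- Reconcile the genotype footnote, Section 9.9 and Annex Table 3, and list the promised genotype sensitivity analysis in Table 7.

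The cost is wording and a PS refit that stays blind to outcomes, with a few more parameters and possibly slightly fewer caliper matches. The named minimum is about 10 terms: transfusion count 1, drugs 4, VOC and ACS 2, inpatient and outpatient use 2, hematology care 1. If the Table 6 overfit criterion is read as 12 exposed patients per covariate, that needs 10 × 12 = 120, within the 185 treated patients of the sample size calculation.

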After applying the inclusion/ exclusion criteria, to determine patient index date, the exposed group will index on the first voxelotor prescription claim date and will be sequentially matched using CEM with up to four non-voxelotor patients based on exact age (year) and calendar date to achieve balance between groups. ¹⁸ All exposed patients will be sampled before selecting control patients so that there will be no potential for voxelotor patients to be included in the control group. Age is a critical matching criterion, as individuals with SCD have better access to care before adulthood and accumulate comorbidities through the natural course of the disease. ¹⁹ The matched controls will be selected from the pool of patients who meet all the eligibility criteria below and are the same age (year) on the same day as the

voxelotor claim. Depending on available matches on the same date as the voxelotor claim, an age caliper may be considered to preserve sample size.

Voxelotor individuals will be matched in chronological order where up to four referent non-voxelotor controls will be identified for each voxelotor individuals before additional referent non-voxelotor matches are identified for the remaining exposure group individuals. Individuals will be sampled once to either the matched voxelotor or non-voxelotor cohort and contribute to one group only. This matching approach ensures that all referent individuals are matched to a voxelotor patient on the same date, mitigating potential selection bias by controlling for calendar time and thus any secular trends in available therapies, clinical guidelines, and other confounders that may occur during the study period (e.g., COVID-19 pandemic). Available matches depend on the number of eligible individuals available in the data source.

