Multiple PS methods will be considered and a step-wise approach will be used to select the most appropriate method. PS matching, in which voxelotor-exposed individuals are matched to unexposed patients using variable-ratio (1:2) greedy nearest neighbor matching with a caliper, will be the primary approach.³¹ If the sample size falls below the minimum required sample size for the primary and secondary endpoint to be 80% powered during the matching process, weighting methods, such standardized mortality/morbidity ratio (SMR) weights, will be evaluated for their suitability and to preserve sample size of the exposed group. With the SMR approach, weights for the voxelotor group are equal to 1; weights for the referent arm are defined as PS/(1-PS). The distribution of SMR weights will be reviewed; truncation and trimming will be considered to account for extreme weights. If neither PS model type is deemed appropriate, a non-ATT model (overlap weights) will be considered. With the overlap approach, overlap weights are defined as 1-PS in the voxelotor arm; weights for individuals in the referent arm are defined as the PS. The distribution of overlap weights will be reviewed to evaluate the appropriate trimming threshold. PS-matching and weighting methods will be further described in the SAP.

Diagnostic Evaluation of PS Methods

An *a priori* list of diagnostic criteria will be set to ensure analytic assumptions are met before a PS method is selected. For example, ASD will be used to assess the comparability of the groups before and after the application of PS methods.³² Observations for any covariate leading to zero cells in either group may lead to an inadequate overlap between groups in

their PS distributions. Therefore, collapsing similar categories within variables if there are categories with frequencies <10% to minimize concerns for non-positivity will be considered. Further, variables with substantial non-positivity may be removed from the model (i.e., covariables with very low or zero values in either group). Patients with missing information for covariables may be excluded or imputed from the analysis set depending on the degree of missingness and the variable. When applicable, a robust variance estimator may be utilized in the outcome model(s) to account for the weighted design. Demographics and baseline clinical characteristics of patients within each study group will be described before and after the applications of PS adjustment.

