Unmeasured confounding leading to an unobservable imbalance between the voxelotor, and referent groups may be present given not all demographic or clinical characteristics are available in the KHM database (e.g., race or ethnicity, provider characteristics, genotypes, etc.). The study population will consist of voxelotor patients who are able to be linked to proprietary claims and with standardized fields for demographic variables that may not be as generalizable (e.g., specific race or ethnic populations like 'Middle Eastern' are not reflected in claims). The COVID-19 pandemic will overlap with the study period, however, the impact on healthcare utilization is expected to be equal among the exposed and control groups. Adherence to voxelotor will be assumed with each prescription fill per the days supply. If patients are not adherent to daily doses of voxelotor, the treatment effect may be underestimated in the exposed population. However, these limitations are inherent to the data source and thus cannot be addressed in this study.

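### Calendar time is matched only before the propensity-score step, so the claimed control of secular trends is neither guaranteed nor checked in the analysed cohort

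*Protocol*

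**What the plan says.** Section 9.2 builds the control pool. Each voxelotor patient is "sequentially matched using CEM with up to four non-voxelotor patients based on exact age (year) and calendar date to achieve balance between groups". The order is fixed: "Voxelotor individuals will be matched in chronological order where up to four referent non-voxelotor controls will be identified for each voxelotor individuals". Each person is sampled once. The section then states the benefit: "This matching approach ensures that all referent individuals are matched to a voxelotor patient on the same date", thereby "mitigating potential selection bias by controlling for calendar time and thus any secular trends in available therapies, clinical guidelines, and other confounders", with the pandemic given as an example.

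Section 9.7.2 then works on that pool. In the primary approach, "voxelotor-exposed individuals are matched to unexposed patients using variable-ratio (1:2) greedy nearest neighbor matching with a caliper". If too few patients remain, SMR weights are used, with the referent weight set to the odds of the PS; if that also fails, overlap weights. None of the three carries a term for CEM set or index date. Further detail is deferred to the SAP.

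Table 4, the list of possible PS covariates, includes age (the other CEM variable) but no index date, quarter or year. (Section 9.7.2 points to Table 5 for the covariates, but Table 5 holds the endpoints.) Table 6 checks the balance of the covariates.

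For the matched-censoring sensitivity analysis, Table 7 defines the matched set as the PS-matched set. Sections 9.7.3 and 9.9 censor controls on the date their voxelotor match discontinued. Section 9.9 adds, on COVID-19, that "the impact on healthcare utilization is expected to be equal among the exposed and control groups".

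**The concern.** The statement about secular trends is made for the CEM pool, but the estimate comes from the cohort after PS matching or weighting. That step may select or reweight controls in a way that shifts their index dates.

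Index dates span November 2019 to January 2023. The primary endpoint is a within-patient change between two adjacent years, counted from billed care. If care use or available therapies moved over that window, the expected change depends on the index date. A difference in index-date mix between the arms would then add an era difference to the voxelotor estimate. Because calendar time is not a listed covariate, the Table 6 check would not show the shift, and the rule that adds unbalanced covariates to the outcome regression would not be triggered.

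**Working it through.** **1. Where calendar date appears**

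| Step | Calendar date used? | Age used? |
|---|---|---|
| CEM (9.2) | yes, same day | yes, exact year |
| Covariate list (Table 4) | no | yes |
| PS matching, SMR, overlap (9.7.2) | not stated | through the PS, if selected |
| Balance check (Table 6) | no | yes |

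Of the two CEM variables, only age is checked again after the PS step.

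**2. The plan's own figure.** The protocol gives no figure for calendar balance. Its one design figure is 185 treated and 370 controls. With SD 3.0, difference 1, 80% power and two-sided 5% (assumed; alpha is not stated): n treated = (1 + 1/2) × (1.960 + 0.842)² × 3² / 1² = 106, and 106 × 1.65 = 175. The stated 185 is somewhat conservative (power about 82%). The point does not depend on it; 185 only sets the scale below.

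**3. Simulation of the two steps (all data assumed).** 185 treated; index window of 1,163 days (25 November 2019 to 31 January 2023); CEM with up to four same-date controls; logistic PS; greedy 1:2 matching across CEM sets with a caliper of 0.2 SD of the logit. Entries are the absolute standardized difference in index date, with the share of runs above 0.10 in brackets. Overlap weights were not simulated.

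| CEM sets | PS covariates' link to calendar time | After CEM | PS matching | SMR |
|---|---|---|---|---|
| always four | none | 0.00 | 0.00 (1%) | 0.00 (0%) |
| always four | moderate | 0.00 | 0.05 (12%) | 0.05 (5%) |
| always four | strong | 0.00 | 0.14 (75%) | 0.15 (83%) |
| size varies over time | none | 0.19 | 0.18 (95%) | 0.19 (99%) |
| size varies over time | moderate | 0.19 | 0.23 (100%) | 0.24 (100%) |
| size varies over time | strong | 0.18 | 0.30 (100%) | 0.31 (100%) |

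The median gap in index date within PS-matched sets was about 330 to 345 days, against 0 when matching stays within CEM sets. Random pairing of dates spread evenly over the window gives 1,163 × (1 − 1/√2) = 341 days. Same-date pairing is thus lost altogether, while balance of the date distributions may or may not be.

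**4. From imbalance to bias.** Let b be the trend in expected change, in transfusions per patient per year for each calendar year of index. Then bias = standardized difference × SD of index date / 365 × b. With evenly spread dates (assumed), SD = 1,163/√12 = 336 days.
- 0.05: 17 days, bias 0.05b
- 0.14: 47 days, bias 0.13b
- 0.30: 101 days, bias 0.28b

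The documents give no value for b, and a pandemic step would not follow a linear trend.

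**5. Matched censoring.** Suppose a voxelotor patient is indexed on study day 100 and stops on day 300, and the PS-matched control is indexed 340 days later, on day 440. Censoring the control on the calendar date of discontinuation would end follow-up 140 days before it begins. The date-based wording works only if index dates are shared.

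**The case against.** A reader might infer that calendar control fails outright, or that pairing a 2020 patient with a 2022 control is itself biasing. The documents do not support either.

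- Section 9.7.2 restricts the PS step to the treated group and its matched controls, so it starts from a date-matched pool.
- Choosing up to two of the four controls within each CEM set is not excluded. The reason given for version 2.1 in the amendment table is compatible with it, and date-based censoring presupposes it.
- The primary model compares group means. Date-discordant pairs do no harm if the two date distributions agree, and with full sets and at most a moderate link they largely did.
- Section 9.9 states an expectation about COVID-19 as a limitation. It does not claim that CEM delivers pandemic control.

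It is also tempting to put a size on early initiators using up the controls. If early and late patients, split 50/50, received 4 and 3, 4 and 2, or 4 and 1 controls, the pool would be 57%, 67% or 80% early. These ratios are assumptions and describe the pool before PS matching. With at most two controls taken per set, the first two cases could return to 50%. In a toy run of the chronological algorithm with 400 exposed, the index-date difference was 0.20, 0.12, 0.09 and 0.05 for control pools of 600, 1,000, 1,500 and 2,500, so larger pools pass the 0.10 limit. Eligibility is assessed at each index date, so new candidates also enter over time.

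All of this stands against a claim of demonstrated bias. It does not answer the narrower point. Deferral to the SAP covers how matching is done, but the claim of calendar control is made in the protocol, and the protocol's own covariate list and balance check leave out the variable needed to verify it. The weighting formulas are explicit and contain no set or date term, so the fallbacks are unprotected even if PS matching is meant to be within set.

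**Conclusion.** The point holds in limited form. Calendar time is matched at the CEM step only. After PS matching or weighting, its control is neither guaranteed nor checked, and the secular-trend statement in section 9.2 is not established for the analysed cohort.

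Bias requires PS covariates linked to calendar time, or CEM set sizes that change over the index window, together with a real trend in the endpoint. The protocol gives no means of sizing any of these. The simulated range (0.00 to about 0.31 against the plan's limit of 0.10) rests wholly on assumed data. It shows that the check could pass or fail, not which will happen. Separately, the date-based censoring wording in sections 9.7.3 and 9.9 is undefined in effect if index dates differ within a PS-matched set. This is worth correcting because the remedy is nearly free; it does not show that the design fails.

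**What to change.** 1. Add index period to Table 4, as continuous index date or coarse categories. Quarters fit poorly: the window touches 14 of them, so 185/14 is about 13 exposed each. With even uptake (assumed) a full quarter holds 91/1,163 = 8% of patients, and the end fragments of 37 and 31 days about 6 and 5 exposed. That strains the rule of at least 12 exposed per covariate (Table 6) and the collapsing of categories below 10% (section 9.7.2). Six half-years, with the ends merged into their neighbours, give about 31 exposed each.
2. Include it in every PS model (matching, SMR, overlap) regardless of the entry rule. That rule admits only covariates with a difference above 0.1 before PS adjustment, and CEM may have removed that difference. At the least, put it in the outcome model if its difference after PS adjustment exceeds 0.10.
3. Report its balance before and after the PS step under Table 6.
4. State whether PS matching is within CEM set, within index period, or unrestricted. Within-set matching should not be mandatory: in the simulation with full sets it kept only about 60 to 66 of 185 treated (159 to 177 of 500).
5. Define matched censoring in days since index unless index dates are shared, and align section 9.7.3, Table 7 and section 9.9.
6. Limit the calendar-time statement in section 9.2 to the cohort that passes the check.

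The cost is wording, one already available covariate in the PS model, and possibly a few lost matches. Adjustment for index period itself was not simulated.
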